- c. AEs will be collected from the time of informed consent through Day 57 or EOS. Any AEs ongoing at Day 85 or EOS Visit must be followed until resolution or investigator determines the event to be stable. AEs should be assessed at least monthly.
- d. ASP0598 Otic Solution or placebo will be applied onto the remaining tympanic membrane under a microscope with a 22-gauge blunt needle. After ASP0598 Otic Solution or placebo administration, subjects will be required to remain on their side with the treated ear facing up for at least 15 minutes. Please see the Pharmacy Manual, Section 9.4: Dose Administration for detailed instructions.
- e. Otology examinations will be performed for both ears at the screening visit.
- f. Microscopic Ear examination will be performed prior to and 60 (± 5) minutes after ASP0598 Otic Solution/placebo administration. Skin local reaction at the application site will be evaluated by Modified Brighton Grading Scheme (Appendix 12.9) at 60 (± 5) minutes after ASP0598 Otic Solution/placebo administration.
- g. Ear cleaning will not be conducted between Days 2 – 57, unless it is absolutely necessary. Investigators will not clean the treated ear by suctioning unless subjects experience uncomfortable ear discharge.
- h. At Day 1, imaging pictures will be taken at the following time points: pre-dose, immediately after, 30 (± 5) minutes, and 60 (± 5) minutes after the ASP0598 Otic Solution or placebo administration.
- i. At Day 85 or EOS, the whole TM should be visible before taking imaging picture. If the whole TM is not visible, the investigator should clean the ear canal.
- j. Bone conduction testing at Day 15, 29, and 57 will be tested only at 1, 2 and 4 kHz (ototoxicity assessment).
- k. Urine or serum pregnancy test will be performed in women of childbearing potential.

Table 4 Schedule of Assessments – MAD

| | Day | Screening | Randomization | Observation | | | | | | | |
|---|------|--------------------|----------------|----------------|-------------------|----------------|-------------------|----------------|----------------|------------------------------|--|
| | | Day – 28 to Day -1 | Day 1 | Day 8 | Day 15 | Day 22 | Day 29 | Day 36 | Day 57 | Day 85 Last Visit/ EOS | |
| Visit Windows | Week | | | Week 1 | Week 2 | Week 3 | Week 4 | Week 5 | Week 8 | Week 12 | |
| Visit number | | 1 | 2 | 3 | 4 | 5 | 6 | 7 | 8 | 9 | |
| Study Procedures | | | | | | | | | | | |
| Informed Consent | | X | | | | | | | | | |

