- d. ASP0598 Otic Solution or placebo will be applied onto the remaining tympanic membrane under a microscope with a 22-gauge blunt needle. After ASP0598 Otic Solution or placebo administration, subjects will be required to remain on their side with the treated ear facing up for at least 15 minutes. Please see the Pharmacy Manual, Section 9.4: Dose Administration for detailed instructions.
- e. Otology examinations will be performed for both ears at the screening visit.
- f. Microscopic Ear examination will be performed prior to and 60 (± 5) minutes after ASP0598 Otic Solution/placebo administration. Skin local reaction at the application site will be evaluated by Modified Brighton Grading Scheme (Appendix 12.9) at 60 (± 5) minutes after ASP0598 Otic Solution/placebo administration.
- g. Ear cleaning will not be conducted between Days 2 – 85, unless it is absolutely necessary. Investigators will not clean the treated ear by suctioning unless subjects experience uncomfortable ear discharge).
- h. At Days 1, 15, and 29, imaging pictures will be taken at the following time points: pre-dose, immediately after, 30 (± 5) minutes, and 60 (± 5) minutes after the ASP0598 Otic Solution or placebo administration.
- i. At Day 85 (SAD) or Day 113 (single dose expansion) and/or EOS, the whole TM should be visible before taking imaging picture. If the whole TM is not visible, the investigator should clean the ear canal.
- j. Bone conduction testing at Day 15, 29, 43, 57, and 85 will be tested only at 1, 2 and 4 kHz (ototoxicity assessment).
- k. Urine or serum pregnancy test will be performed in women of childbearing potential.
- l. ASP0598 Otic Solution or placebo administration on Day 15 and Day 29 will be conducted in the case that the TMP closure is not confirmed.

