dose concentration of MAD will be 5.0 µg/mL, and another dose concentration up to a maximum feasible dose concentration of 15 µg/mL will be considered.

The first interim analysis will be conducted after completion of the last SAD cohort. Data will be summarized for all time points available. The second interim analysis will be conducted after completion of the last MAD cohort.

The Data Monitoring Committee (DMC) will review the data and make the final decision to open single and/or multiple dose expansion. The DMC operation, roles and responsibilities will be described in the DMC Charter.

Subjects may be replaced at the discretion of the sponsor. If replaced, the replacement subject will be given the same treatment group the original subject's randomized treatment group.

Dose Expansion

The decision to open single and/or multiple dose expansion will be made based on the safety and efficacy results of the interim analyses after completion of SAD and after completion of MAD by the DMC per the charter. Once the decision to open single and/or multiple dose expansion is made, the number of treatment groups (2 or 3 treatment groups including 1 or 2 active treatment groups and 1 placebo group) and the dose for ASP0598 Otic Solution will be selected based on the safety and efficacy result of the interim analyses. All analyses will be described in the Interim Analysis Plan (IAP).

Up to 39 subjects will be randomized to single dose and/or multiple dose expansion. Based on the interim analysis results:

- If 3 treatment groups are selected, approximately 39 subjects will be randomized in a 1:1:1 ratio of high dose ASP0598 Otic Solution, low dose ASP0598 Otic Solution, or placebo (13 subjects in each treatment group).
- If 2 treatment groups are selected, approximately 26 subjects will be randomized in a 1:1 ratio of high dose ASP0598 Otic Solution or placebo (13 subjects in each treatment group).

Stratification at the time of randomization will be based on the % size of the TMP at the screening visit and subjects will be balanced equally between the treatment groups. Dose expansion will assess safety and efficacy of ASP0598 Otic Solution.

Single Dose Expansion

After randomization on Day 1, subjects will receive ASP0598 Otic Solution or placebo administration into the affected ear at the investigative site. Subjects will return to the investigative site for assessments on Days 15, 29, 57, and 85 (EOS).

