6.3.6 Assignment and Allocation

SAD

In each cohort, a total of 5 subjects will be randomized in a 4:1 ratio of ASP0598 Otic Solution (4 subjects) and placebo (1 subject).

MAD

In each cohort, a total of 8 subjects will be randomized in a 6:2 ratio of ASP0598 Otic Solution (6 subjects) and placebo (2 subjects).

Dose Expansion

- Based on the interim analysis results, if 3 treatment groups are selected, approximately 39 subjects will be randomized in a 1:1:1 ratio of high dose ASP0598 Otic Solution, low dose ASP0598 Otic Solution, or placebo (13 subjects in each treatment group).
- If 2 treatment groups are selected, approximately 26 subjects will be randomized in a 1:1 ratio of high dose ASP0598 Otic Solution or placebo (13 subjects in each treatment group).

Subjects will be stratified at the time of randomization by % size of the TMP ($\leq 15\%$, $> 15\%$) at the Screening Visit. Subjects will be balanced equally between the treatment groups.

TMP size group will be determined by the Screening images sent from the investigative site to the central imaging vendor.

For SAD, MAD, and dose expansion, randomization will be performed via IRT using central allocation. If a subject is assigned a randomization number, but does not receive study drug, the randomization number will not be used again. The randomization schedule that determines subject treatment will be computer-generated by IRT before the beginning of the study. The unblinded study site personnel will dispense the treatment according to the IRT system's assignment. Specific procedures for randomization through the IRT are contained in the study-specific IRT manual.

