6.4.2 Analysis of Secondary Efficacy Endpoints

SAD and MAD

No statistical hypothesis testing will be performed.

Single dose expansion

- Subjects with complete closure of TMP at Week 12

Primary Analysis:

At week 12, to understand the relationship between complete closure of TMP and treatment group, MH test adjusting for baseline perforation size group ($\leq 15\%$, $> 15\%$) will be used. Analysis will be performed using the data for the estimand (refer to

Section 5.3 for details) and done separately for each ASP0598 treatment group vs placebo. Here baseline perforation size group is the same as baseline TMP size group per total area of tympanic membrane from central imaging.

From this analysis, the following results will be presented:

- Proportion of subjects with complete closure of TMP in each treatment group (each of ASP0598 treatment group and placebo),
- For the comparisons between each of the ASP0598 treatment group vs placebo, risk difference (ASP0598 – placebo), 2-sided p-value for overall general association between treatment group and response and 2-sided 95% stratified Newcombe Confidence Interval (CI) computed using MH weights for the risk difference. If the CI cannot be obtained using Newcombe method then they will be presented using Sato method.

If the Mantel and Fleiss criterion (across-strata sum of expected values for a particular cell has a difference of at least 5 from both the minimum possible sum and the maximum possible sum of the observed values) is not satisfied, the above analysis will be performed with no stratification factor and exact p-value using Fisher-exact method and CI using Clopper-Pearson method will be presented.

Based on the interim analysis results, if 3 treatment groups are selected for the dose expansion phase, hierarchical testing method will be used to control familywise error rate where the highest dose group vs placebo will be tested first at a 2-sided significance level of 0.05 and if the null hypothesis is rejected for this comparison, low dose group vs placebo will be tested at a 2-sided significance level of 0.05.

Sensitivity analysis:

The above analysis will be repeated using sensitivity analysis imputation definition.

- Change from baseline in the ratio of TMP size per total area of tympanic membrane at Week 12
- Change from baseline in TMP size at Week 12

Primary analysis:

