6.9.2.2 Analysis Visit Windows

Table 6 Analysis Visit Windows: Imaging

Analysis Visit	Target Study Day	Analysis Visit Window (Study Day)			
		SAD	Single dose expansion	MAD	Multiple dose expansion
Baseline ^a	1	≤ 1	≤ 1	≤ 1	≤ 1
Day 2 ^b	2	2	NA	NA	NA
Day 2 ^c	2	2 to 3	NA	NA	NA
Day 3 ^d	3	3 to 4	NA	NA	NA
Week 1	8	5 to 11	NA	2 to 11	NA
Week 2	15	12 to 18	2 to 18	12 to 18	2 to 22
Week 3	22	NA	NA	19 to 25	NA
Week 4	29	19 to 39	19 to 39	26 to 32	23 to 36
Week 5	36	NA	NA	33 to 39	NA
Week 6	43	NA	NA	NA	37 to 50
Week 8	57	≥ 40	40 to 74	40 to 74	51 to 71
Week 12	85	NA	≥ 75	≥ 75	72 to 99
Week 16	113	NA	NA	NA	≥ 100
EOS ^e		≥ 2	≥ 2	≥ 2	≥ 2

For the results corresponding to post-dose timepoints immediately after, 0.5 hour and 1 hour post-dose on the dosing days, analysis timepoint will be assigned same as the nominal timepoint and these results will not be used to identify the value for analysis.

^a Baseline value for the above data is based on the last available non-missing value on or prior to the first dose day (Day 1) of study drug within the visit window.

^b For cohorts 1, 2 and 3.

^c For cohorts 4, 5 and 6.

^d Day 3 evaluations will only be performed for cohorts 1, 2 and 3.

^e EOS value for the above data is based on the last available non-missing post-baseline value within the visit window.

Table 7 Analysis Visit Windows: PTA Assessments, Tympanometry and Tympanogram

Analysis Visit	Target Study Day	Analysis Visit Window (Study Day)			
		SAD	Single dose expansion	MAD	Multiple dose expansion
Baseline ^a	1	≤ 1	≤ 1	≤ 1	≤ 1
Week 8	57	≥ 40	NA	NA	NA
Week 12	85	NA	≥ 75	≥ 75	72 to 99
Week 16	113	NA	NA	NA	≥ 100
EOS ^b		≥ 2	≥ 2	≥ 2	≥ 2

^a Baseline value for the above data is based on the last available non-missing value on or prior to the first dose day (Day 1) of study drug within the visit window.

^b EOS value for the above data is based on the last available non-missing post-baseline value within the visit window.

To identify the value for the analysis, the following rules will apply excluding baseline and EOS:

1. For an analysis visit, if a subject has more than one result included within a window, the value closest to the target study day will be used. In case of ties between values located on different sides of the target study day, the later assessment will be used.

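### The closure test is stratified by the baseline (normally Day 1) perforation size group, not the Screening size group used to randomise; validity and power are unaffected, but the stratified test is abandoned more often

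*SAP*

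**What the plan says.** **Randomisation.** Protocol 4.1 states: "Stratification at the time of randomization will be based on the % size of the TMP at the screening visit". Protocol 6.3.6 gives the cut (≤15%, >15%) and the source: "TMP size group will be determined by the Screening images sent from the investigative site to the central imaging vendor".

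**Analysis.** Protocol 9.4.2.1 and SAP 6.4.2 test complete closure at Week 12 (single dose expansion) with an MH test adjusted for baseline perforation size group. The Week 16 test (multiple dose expansion) refers back to it. SAP 6.4.2 then defines the group: "Here baseline perforation size group is the same as baseline TMP size group per total area of tympanic membrane from central imaging". If the Mantel-Fleiss criterion is not met, the stratification is dropped and Fisher's exact test is used, with a different confidence interval method.

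**What baseline means for images.** SAP 6.9.2.2, Table 6, footnote a: "Baseline value for the above data is based on the last available non-missing value on or prior to the first dose day". Of the images taken after dosing on a dosing day, Table 6 says "these results will not be used to identify the value for analysis". Both expansions schedule a pre-dose image on Day 1. The single dose schedule in protocol 1.3 reads "At Day 1, imaging pictures will be taken at the following time points: pre-dose, immediately after" and the multiple dose schedule reads "At Days 1, 15, and 29, imaging pictures will be taken at the following time points: pre-dose, immediately after".

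**Two variables.** SAP 6.2.3 lists the stratification factor size group and the baseline central-imaging size group as separate characteristics, both cut at 15%. The subgroup list in the text of SAP 6.4 also carries both.

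**The concern.** The usual practice is to analyse by the strata used to randomise, because that is where the design forces balance between arms. Here the SAP has that variable and selects the other one, without giving a reason. A subject whose ratio lies near 15% can be in one group at Screening and in the other on Day 1, up to 28 days later.

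This could matter more than usual for two reasons. Complete closure is the only efficacy endpoint with a familywise error procedure, and each comparison has 13 subjects per arm. The stratum definition also feeds the Mantel-Fleiss check, so it helps to decide which test and which confidence interval are reported. No test on the randomised stratum is planned; that factor appears only in descriptive summaries.

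**Working it through.** **1. Which reading is used.** The randomisation stratum is the central read at Screening (Day −28 to −1). The analysis stratum is the last non-missing central read on or before Day 1, with post-dose images excluded. Because a Day 1 pre-dose image is scheduled, the analysis stratum is the Day 1 reading unless that is missing, in which case it reverts to Screening. SAP 6.4.2 does not itself mention Day 1; this follows from Table 6 and the imaging schedule.

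**2. The plan's sample size.** Inputs from protocol 9.1: 10% vs 80%, two-sided 0.05, more than 90% power, 10% dropout.
- Normal approximation: 9 per group without continuity correction, 11 with it.
- Exact Fisher power: 84.1% at 10, 90.5% at 11, 97.0% at 13 per group.
- Dropout: 11/0.9 = 12.2, rounded up to 13.

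The stated 11 and 13 are reproduced. The calculation is unstratified, so the choice of stratum does not alter it.

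**3. How close the Mantel-Fleiss criterion is.** In stratum k let there be n1 active and n0 placebo subjects, N in total, and m closures. Then E = Σ n1·m/N, L = Σ max(0, m − n0), U = Σ min(n1, m). The criterion is min(E − L, U − E) ≥ 5. With equal arms within each stratum it becomes Σ min(m, N − m) ≥ 10, so it needs at least 10 and at most 16 closures among 26. The planning rates predict 13 × 0.10 + 13 × 0.80 = 11.7, which is 1.7 above the lower limit.

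One subject changing group can then switch the test. For illustration, take strata of 6+6 and 7+7 subjects (active + placebo) with 5 closures each: E = 2.5 + 2.5 = 5.0, L = 0, U = 10, and the criterion is met. Move one closed active subject from the first to the second:
- First stratum: 5+6 subjects, 4 closures, E = 5 × 4/11 = 1.818.
- Second stratum: 8+7 subjects, 6 closures, E = 8 × 6/15 = 3.200.
- Total E = 5.018, U − E = 10 − 5.018 = 4.982, and the criterion fails.

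**4. Simulation with a fixed share changing group.** The documents give no share, so 5%, 10% and 20% are assumed. In a 26-subject comparison that is 1.3, 2.6 or 5.2 subjects expected, with a 74%, 94% or 99.7% chance of at least one. Further assumptions: 50:50 strata, blocks of 2, closure shifted by ±10 points according to baseline group, 5,000 trials per row. Results at 13 per group, where power is for the full procedure including the Fisher fallback:

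| Share changing group | Criterion met, Screening strata | Criterion met, baseline strata | Power, Screening | Power, baseline |
|---|---|---|---|---|
| 0% | 51.6% | 51.6% | 97.6% | 97.6% |
| 5% | 54.0% | 39.4% | 97.3% | 97.3% |
| 10% | 57.6% | 33.5% | 97.3% | 97.2% |
| 20% | 63.8% | 28.7% | 97.3% | 97.3% |

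At 11 per group, power is 91–92% with either set of strata. The criterion is met in 14–18% of trials with Screening strata and 4–8% with baseline strata. Type I error of the full procedure at 13 per group is 0.3–0.6% for a common closure rate of 10% and 2.0–2.7% for 45%, with either set of strata.

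**5. Simulation from a measurement model.** Assumed: lognormal ratio with median 15% and log SD 0.6, and an image-to-image CV of 5%, 10% or 20%. About 4%, 7% and 14% of subjects change group, or 26 × 0.04 = 1.0 to 26 × 0.14 = 3.6 subjects per comparison. With the ±10-point shift, the criterion is met in about 50–60% of trials with Screening strata against 31–42% with baseline strata, and the test that is run differs in 15–35% of trials. Allowing a shift of either 0 or 10 points, the ranges widen to about 48–73% and 31–63%. The gap remains when size has no effect on closure.

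**The case against.** The other side has a good deal to say.

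- **The SAP follows the protocol.** The protocol synopsis and 9.4.2.1 both specify baseline perforation size, and protocol section 9 defines baseline as the last non-missing observation on or before dosing. A reader might infer that the SAP contradicts the protocol's analysis plan. It does not; the mismatch is with the randomisation factor. This stands, and it means the protocol wording must change too.
- **Stratifying on a pre-treatment covariate is legitimate.** A reader might infer that the closure test is biased or invalid. The documents do not support that: both readings are central and pre-dose, and post-dose images are excluded. Nor is there a loss of power. For the MH test alone, baseline strata do marginally better (98.9–99.2% against 98.4–98.8%).
- **The fallback is frequent anyway.** With identical strata the criterion already fails in about half of trials at 13 per group. Small numbers are the main cause, and restoring the randomised strata does not remove it. The fallback is itself a pre-specified exact test.
- **The size rests on assumed inputs.** A median placed exactly at the cut maximises crossing, and 50:50 strata and the block size are also assumptions. The true share could be near zero.
- **The discordance will be visible.** Both factors are tabulated by arm, and closure is summarised by each. The endpoint is secondary in a trial whose primary endpoints are safety.

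These points limit the consequence. None of them gives a reason for preferring the baseline group, and the SAP offers none.

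**Conclusion.** The mismatch is established from the documents: subjects are randomised on the Screening size group and the closure test is stratified on the baseline group, normally the Day 1 pre-dose reading. It affects only subjects whose ratio crosses 15% between the two readings.

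The consequence is modest. Power stays at about 97% at 13 per group and type I error below 5%. What is lost is guaranteed arm balance within the analysis strata, together with some of the trials in which the planned stratified test could have been reported. The size of that loss rests wholly on the assumed 4–14% crossing rate, the closure rates of 10% and 80%, and the assumed strata and blocks. This is an improvement to adopt because it costs almost nothing, not a defect that undermines the closure result.

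**What to change.** In SAP 6.4.2 and Table 3, define the MH stratification variable as the randomisation factor, the Screening perforation size group (≤15%, >15%). Make the same change in the protocol synopsis and 9.4.2.1; amending the SAP alone would create a new disagreement between the two documents. Keep the baseline central-imaging group as a supportive MH analysis and as the subgroup already planned. If the sponsor prefers the baseline group for the main test, state the reason and add the randomised-stratum analysis alongside it. Either way, settle the choice before unblinding, so that neither the stratum nor the resulting test can appear to have been chosen after seeing the data.

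The cost is wording in both documents and a change of variable in the analysis program. The variable already exists in SAP 6.2.3. No new data are needed and the sample size is unchanged.

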6.4.3 Analysis of Exploratory Endpoints

Continuous endpoints:

SAD and MAD

No statistical analysis will be performed.

For the mean air conduction hearing loss group, a shift table of category changes from baseline value to post baseline value at each analysis visit (Week 8 and EOS for SAD, Week 12 and EOS for MAD) will be presented.

Dose expansion

- Change from baseline in the ratio of TMP size per total area of tympanic membrane for post baseline visits at Week 2, Week 4, and Week 8 for single dose expansion

- Change from baseline in TMP size for post baseline visits at Week 2, Week 4, and Week 8 for single dose expansion
- Change from baseline in the ratio of TMP size per total area of tympanic membrane for post baseline visits at Week 2, Week 4, Week 6, Week 8, and Week 12 for multiple dose expansion
- Change from baseline in TMP size for post baseline visits at Week 2, Week 4, Week 6, Week 8, and Week 12 for multiple dose expansion

The above change from baseline dose expansion phase endpoints will be analyzed using the MMRM model as described in Section [6.4.2](#) Single Dose Expansion.

To understand the relationship between change from baseline in the ratio of TMP size per total area of tympanic membrane and mean A-B gap at Week 12 for single dose expansion and Week 16 for multiple dose expansion, linear regression will be used with change from baseline in mean A-B gap as response and change from baseline in the ratio of TMP size per total area of tympanic membrane as predictor variable. A scatter plot with linear regression line, regression equation and 95% CI for the slope will be provided.

For the mean air conduction hearing loss group, a shift table of category changes from baseline value to post baseline value at each analysis visit (Week 12 and EOS for single dose expansion, Week 12, Week 16 and EOS for multiple dose expansion) will be presented.

Categorical endpoints:

Refer to Section [5.4](#) for the list of categorical endpoints. No statistical analysis will be performed.

